# 8.7 Pharmacokinetics

PK samples will be collected at the time points defined in the Assessment schedule (Section 8.1). Follow instructions outlined in the Site Operations Manual regarding sample collection, numbering, processing and shipment. See Section 8.9 regarding the potential use of residual samples.

In order to better define the PK profile, the timing of the PK sample collection may be altered based on emergent data. The number of samples/blood draws and total blood volume collected will not exceed those stated in the SOM. If patients experience suspected immunologically-related AE such as infusion-related reaction, hypersensitivity, cytokine release syndrome and anaphylaxis (as defined by Sampson criterion #1; Sampson et al 2006), an unscheduled PK blood sample should be obtained as close as possible to the event occurrence. The date and time of the last dose and the time of PK blood draw should be recorded.

An ELISA based assay will be used to analyze the CMK389 concentration in PK samples. Commerically Confidential Information

PK samples will be obtained and evaluated in all subjects, all samples will be analyzed except the placebo group.

Commerically Confidential Information

For standard PK abbreviations and definitions see the list provided at the beginning of this protocol.

The following PK parameters will be determined using the actual recorded sampling times and non-compartmental analysis using Phoenix WinNonlin: Ctrough, Cmax, Tmax, and if feasible AUC0-t, AUCinf, t1/2, Vz and CL from CMK389 serum concentration-time data.

The linear trapezoidal rule will be used for AUC calculation. Regression analysis of the terminal plasma elimination phase for the determination of t1/2 will include at least 3 data points after Cmax. If the adjusted R^2 value of the regression analysis of the terminal phase will be less than 0.75, no values will be reported for t1/2, AUCinf and CL.

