### Safety Follow-up Epoch

After the treatment epoch, the safety follow-up epoch will last 12 weeks. This enables the assessment of safety in adults with sarcoidosis for ~5 half-lives following the last administration of CMK389. During the safety follow-up epoch, physical exam, adverse events, safety labs, PK and CCI samples, CCI will be collected every four weeks. During the safety follow-up epoch, treatment for sarcoidosis will be guided by the Investigator; if necessary, methotrexate and/or azathioprine may be reintroduced and corticosteroid doses may be adjusted.

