# 6.2 Treatment arms

Subjects will be assigned to one of the following 2 treatment arms in a ratio of 1:1.

Study treatments are defined as:

- four doses of CMK389 10 mg/kg i.v. (one dose q4 weeks)
- four doses of matching placebo i.v. (one dose q4 weeks)

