# 6.5 Treating the subject

CMK389 will be administered to the subject via i.v. infusion for approximately one hour at the study site. See the pharmacy manual for further details.

Sponsor qualified medical personnel will be readily available to advise on trial related medical questions or problems.

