PK blood collection CCI					X 	X 	X 	X 	X 		X 	X 		X 	X 	X 	x	х	х	x
						Com	mercial	ly Co	nfident	ial Info	rmatio	on		•				•		

Adverse Events					Х						
Study/Epoch completion information	х	x							x		х

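### The linear trapezoidal rule across 28-day sampling gaps overstates AUC by about 6%, and up to about 11%, under mono-exponential decline, and understates clearance to match

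*Protocol*

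**What the plan says.** Protocol 8.7 plans "non-compartmental analysis using Phoenix WinNonlin" on actual sampling times. It lists Ctrough, Cmax and Tmax, "and if feasible AUC0-t, AUCinf, t1/2, Vz and CL from CMK389 serum concentration-time data". On integration it says: "The linear trapezoidal rule will be used for AUC calculation". It gives no separate rule for falling concentrations. The half-life regression "will include at least 3 data points after Cmax", and t1/2, AUCinf and CL are not reported if the adjusted R² is below 0.75.

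The infusion lasts about one hour (Protocol 6.5), given every four weeks for four doses (6.2). Table 8-1 places PK samples:

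- before and 60 minutes after the start of each dose;
- at 180 minutes for doses 1 and 4 only;
- then on Days 113, 141, 169 and 197.

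No half-life is stated in the visible text. The nearest statement is in Protocol 3.1, on the safety follow-up epoch: "This enables the assessment of safety in adults with sarcoidosis for ~5 half-lives following the last administration of CMK389".

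Protocol 11.5.3 summarises all PK parameters descriptively by dose. The PK endpoints named in Protocol 2.2 and SAP 1.3.2 are Cmax/end of infusion and Ctrough. The visible parts of SAP 5.1 and 5.2 name no AUC rule; both are partly redacted.

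**The concern.** Almost all of each AUC is interpolated across gaps of 28 days. The plan fits a terminal phase to obtain t1/2, so it already presumes exponential decline. An exponential decline is convex, and the chord between two points on it lies above it everywhere. The planned rule therefore errs in the same direction in every subject, and averaging over subjects does not remove the error. AUC0-t and AUCinf are too high. CL, which is dose divided by AUC, is too low, and so is Vz.

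What is at stake is the accuracy of descriptive exposure and clearance figures in the study report.

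**Working it through.** The documents give no AUC, clearance or bias figure, so there is nothing to reproduce.

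**Inputs**

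- Sampling gap τ = 28 days (Table 8-1, nominal days).
- Last dose Day 85, last PK sample Day 197: 197 − 85 = 112 days.
- Half-life, inferred from the five-half-lives statement: 112/5 = 22.4 days if counted from the last dose; 84/5 = 16.8 days if only the 12-week epoch is meant.
- Gap in half-lives: 28/22.4 = 1.25; 28/16.8 = 1.67.

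**Closed form, mono-exponential decline**

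Let k = ln2/t1/2 and let C be the concentration at the start of a gap.

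- Linear rule: τ·C·(1 + e^(−kτ))/2.
- True area: C·(1 − e^(−kτ))/k.
- Ratio: x·coth(x), with x = kτ/2 = ln2 × 28/(2 × t1/2).

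| Half-life (days) | x | Linear/true AUC | AUC error | CL error |
|---|---|---|---|---|
| 22.4 | 0.433 | 1.062 | +6.2% | −5.8% |
| 16.8 | 0.578 | 1.109 | +10.9% | −9.8% |

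The CL error is 1/ratio − 1. The ratio exceeds 1 for any half-life.

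**Check on the actual schedule**

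Four one-hour infusions were simulated with the Table 8-1 sampling times and compared with the exact integral:

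| Dose 4 quantity | Linear, 22.4 d | Linear, 16.8 d | Linear-up/log-down |
|---|---|---|---|
| AUC over 112 days | +6.1% | +10.8% | 0.0% |
| AUCinf | +5.9% | +10.7% | 0.0% |

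**If there is a distribution phase (assumption, not from the documents)**

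Take an early phase with a 2-day half-life carrying 30% to 50% of the initial concentration, followed by a terminal half-life of 16.8 to 22.4 days. Dose 4 AUCinf is then overstated by 14% to 38% with the linear rule and by 6% to 16% with linear-up/log-down. The log rule at least halves the error but does not remove it, because nothing is sampled while the early phase runs.

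**Residue in AUCinf after dose 4**

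The requirement of three points after Cmax cannot realistically be met before dose 4. After dose 1, with Cmax at 60 minutes, only the 180-minute and Day 29 pre-dose samples remain. AUCinf from dose 4 also contains drug from doses 1 to 3. Under mono-exponential decline its ratio to Dose/CL is the sum of 2^(−28n/t1/2) for n = 0 to 3:

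- 22.4 days: 1 + 0.420 + 0.177 + 0.074 = 1.67.
- 16.8 days: 1 + 0.315 + 0.099 + 0.031 = 1.45.

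A CL computed as Dose/AUCinf there would be low by 1 − 1/1.67 = 40% or 1 − 1/1.45 = 31%, whichever trapezoidal rule is used.

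**The case against.** The strongest reply is that little depends on this. AUC and CL are computed only if feasible and summarised descriptively. They are not named endpoints, PK/PD analysis is marked not applicable (Protocol 11.5.4), and placebo samples are not analysed, so no comparison between arms is touched. Concentrations are listed and actual times recorded, so anyone can recompute AUC later. All of this stands, and it makes the point minor. It does not make the planned rule accurate.

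The plain reading of the follow-up sentence counts from the last administration, so 22.4 days and about 6% is the central case. The 11% figure needs the narrower reading. That stands too.

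Protocol 8.7 also lets PK sampling times change on emergent data, and redacted SAP text may address AUC. Neither gives a visible denser schedule or a different rule.

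Three stronger readings are tempting and are not supported:

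- A reader might infer that biased AUC and CL would feed dose selection for a later study. No visible text gives them that role. There is one active dose level, and the visible rationale in Protocol 3.3 rests on maximum feasible dose, modelled interferon-gamma inhibition, trough relative to EC80, and peak.
- A reader might infer an error of about a third from Protocol 3.3, which predicts a peak near 440 µg/mL and troughs about 50 times an EC80 of 7.4 nM (370 nM). With an assumed molecular weight of 145 to 150 kDa the trough is 54 to 56 µg/mL, an eightfold fall, and linear AUC would exceed log AUC by 33% to 34%. The molecular weight is not in the documents, and the visible text does not say that this peak and trough belong to one dosing interval.
- A reader might infer that the log rule makes AUC and CL sound. It is exact only for mono-exponential decline, and it does nothing about residue from earlier doses.

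**Conclusion.** The point holds as a minor one. With 28-day gaps, the rule in Protocol 8.7 overstates AUC0-t and AUCinf by about 6% at a half-life of 22.4 days and by up to about 11% at 16.8 days. The integration error alone lowers CL by about 6% to 10%. These sizes rest on mono-exponential decline and on a half-life inferred from the approximate five-half-lives statement. The direction holds for any exponential decline. The error is larger if there is a distribution phase, by an amount the documents do not allow one to fix.

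Cmax/end of infusion and Ctrough are read directly from samples, t1/2 comes from regression, and the efficacy analysis uses no AUC, so none of these changes.

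**What to change.** In Protocol 8.7, replace the linear trapezoidal rule with the linear-up/log-down trapezoidal rule for AUC0-t and AUCinf.

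State in the report that:

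- AUC and CL rest on 28-day sampling gaps, so some upward bias in AUC may remain if there is a distribution phase;
- AUCinf after dose 4 includes residue from doses 1 to 3, and should not be used as Dose/AUCinf for CL without accounting for it.

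The cost is one amended sentence (Protocol 13.1 requires a written amendment), a software setting, and two sentences in the report. No extra sample, visit or blood volume is needed.

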### 8.7.1 PK blood collection

For PK assessment, pre-dose blood samples will be collected before each dose administration. Blood samples will also be collected at designated time points after dosing.

For details on PK blood collection and processing, labeling, and shipment instructions, see laboratory manual.

The exact clock time of dosing, as well as actual sample collection date and time will be entered on the PK blood collection summary page of the CRF. Sampling problems will be noted in the relevant field of the CRF.

## 8.8 Other assessments

Commercially Confidential Information

As outlined in Section 4.1 Inclusion Criteria, investigator must assess the Scadding stage II, III or IV as determined by the most recent chest x-ray obtained within 12 months prior to screening. If necessary, the chest x-ray may be obtained during screening. Original x-ray film, appropriately labeled, will be archived at study site.

## 8.8.2 High Resolution CT of Chest

An HRCT scan of the lung will be completed at screening to assess reticular pattern for the purpose of fulfilling eligibility criteria. The HRCT scans, without contrast agent, will be acquired at full inspiration according to parameters as listed in a separate imaging acquisition manual. Inclusion scans will be read by a central reader (expert radiologist) contracted through imaging vendor. The total whole body effective dose per subject from the HRCT scanning (excluding [F]FDG-PET/CT) will be maximally 4 mSv.

An historical HRCT obtained within 12 months from screening may also be sent to the central reader for over-read.

Refer to the Imaging Acquisition Guidelines and Imaging Investigator Site Operations Manual for HRCT details and requirements for historical HRCT.

The coded medical images will be used primarily for analysis as described in this protocol; however, the images may also be used for the development and evaluation of new analysis methods directly related to the area of research that this study covers. Incidental findings are beyond the scope of central imaging vendor. If an investigator/radiologist recognizes any incidental finding in the images during the course of conducting the clinical trial, the investigator should follow up as part of his/her duty of care to ensure the safety and wellbeing of the participant.

Commercially Confidential Information

### 8.8.4 Fasting lipid panel

A fasting lipid panel will be performed, measuring cholesterol, direct LDL, HDL cholesterol, LDL cholesterol, and triglycerides.

Sample(s) will be collected at the timepoint(s) defined in the Assessment schedule (Section 8.1). Detailed instructions for sample collection, numbering, processing and shipment will be provided in the Central Lab Manual.

Confidential

Commercially Confidential Information

## 8.9 Use of residual biological samples

Residual blood and urine samples may be used for another protocol specified endpoint. Commercially Confidential Information Commercially Confidential Information

# 9 Safety monitoring

#### 9.1 Adverse events

An adverse event (AE) is any untoward medical occurrence (i.e., any unfavorable and unintended sign [including abnormal laboratory findings], symptom or disease) in a subject after providing written informed consent for participation in the study until the end of study visit. Therefore, an AE may or may not be temporally or causally associated with the use of a medicinal (investigational) product.

AEs of Special Interest comprise hypersensitivity reactions such as serum sickness and anaphylaxis (as defined by Sampson criterion #1; Sampson et al 2006).

In addition, all reports of intentional misuse and abuse of the study treatment are also considered an adverse event irrespective if a clinical event has occurred. See Section 9.5 for an overview of the reporting requirements.

The occurrence of adverse events must be sought by non-directive questioning of the subject at each visit during the study. Adverse events also may be detected when they are volunteered by the subject during or between visits or through physical examination finding, laboratory test finding, or other assessments.

Abnormal laboratory values or test results constitute adverse events only if they fulfill at least one of the following criteria:

- they induce clinical signs or symptoms,
- they are considered clinically significant,
- they require therapy.

Clinically significant abnormal laboratory values or test results should be identified through a review of values outside of normal ranges/clinically notable ranges, significant changes from baseline or the previous visit, or values which are considered to be non-typical in patients with underlying disease. Investigators have the responsibility for managing the safety of individual subject and identifying adverse events. Alert ranges for liver and kidney related events are included in Appendix 1 and Appendix 2, respectively.

Adverse events should be recorded on the Adverse Events CRF under the signs, symptoms or diagnosis associated with them, and accompanied by the following information:

- 1. The severity grade
  - a. Adverse events will be primarily assessed and graded according to the "Toxicity Grading Scale for Healthy Adult and Adolescent Volunteers Enrolled in Preventive Vaccine Clinical Trials". A copy of the Toxicity Grading Scale can be found in the Investigator Portal.

b. For any adverse event not listed in the "Toxicity Grading Scale for Healthy Adult and Adolescent Volunteers Enrolled in Preventive Vaccine Clinical Trials", the adverse event will be assessed and graded according to the "Common Terminology Criteria for Adverse Events", version 5.0 (CTCAE v5.0). A copy of the CTCAE Grading Scale can be found in the Investigator Portal.

Confidential

- c. For infusion-related reactions, event will also be assessed and graded according to the CTCAE v5.0
- 2. Its relationship to the study treatment
  - Yes or
  - No
- 3. Its duration (start and end dates) or if the event is ongoing an outcome of not recovered/not resolved must be reported.
- 4. Whether it constitutes a SAE (see Section 9.2 for definition of SAE) and which seriousness criteria have been met
- 5. Action taken regarding investigational treatment.

All adverse events must be treated appropriately. Treatment may include one or more of the following:

- no action taken (e.g. further observation only)
- investigational treatment dosage increased/reduced
- investigational treatment interrupted/withdrawn
- concomitant medication or non-drug therapy given
- hospitalization/prolonged hospitalization (see Section 9.2 for definition of SAE)

Information about common side effects already known about the investigational drug can be found in the Investigator's Brochure (IB) or will be communicated between IB updates in the form of Investigator Notifications. Once an adverse event is detected, it must be followed until its resolution or until it is judged to be permanent, and assessment should be made at each visit (or more frequently, if necessary) of any changes in severity, the suspected relationship to the investigational drug, the interventions required to treat it, and the outcome.

The investigator must also instruct each subject to report any new adverse event (beyond the protocol observation period) that the subject, or the subject's personal physician, believes might reasonably be related to study treatment. This information must be recorded in the investigator's source documents; however, if the AE meets the criteria of an SAE, it must be reported to Novartis.

\*Refer to the Site Operations Manual for data capture methodology regarding AE collection for subjects that fail screening.

# 9.2 Serious adverse event reporting

# 9.2.1 Definition of SAE

An SAE is defined as any adverse event (appearance of (or worsening of any pre-existing) undesirable sign(s), symptom(s) or medical conditions(s)) which meets any one of the following criteria:

- is fatal or life-threatening
- results in persistent or significant disability/incapacity
- constitutes a congenital anomaly/birth defect
- requires inpatient hospitalization or prolongation of existing hospitalization, unless hospitalization is for:
  - routine treatment or monitoring of the studied indication, not associated with any deterioration in condition
  - elective or pre-planned treatment for a pre-existing condition that is unrelated to the indication under study and has not worsened since the start of study drug
  - treatment on an emergency outpatient basis for an event not fulfilling any of the definitions of a SAE given above and not resulting in hospital admission
  - social reasons and respite care in the absence of any deterioration in the subject's general condition
- is medically significant, e.g. defined as an event that jeopardizes the subject or may require medical or surgical intervention.

All malignant neoplasms will be assessed as serious under "medically significant" if other seriousness criteria are not met.

Life-threatening in the context of a SAE refers to a reaction in which the subject was at risk of death at the time of the reaction; it does not refer to a reaction that hypothetically might have caused death if it were more severe (please refer to ICH E2D Guideline 2004).

Medical and scientific judgment should be exercised in deciding whether other situations should be considered serious reactions, such as important medical events that might not be immediately life threatening or result in death or hospitalization but might jeopardize the subject or might require intervention to prevent one of the other outcomes listed above. Examples of such events are intensive treatment in an emergency room or at home for allergic bronchospasm, blood dyscrasias or convulsions that do not result in hospitalization or development of dependency or abuse (please refer to ICH E2D Guideline 2004).

Any suspected transmission via a medicinal product of an infectious agent is also considered a serious adverse reaction.

All AEs (serious and non-serious) are captured on the CRF; SAEs also require individual reporting to Novartis Chief Medical Office and Patient Safety (CMO & PS) as per Section 9.2.2.

### 9.2.2 SAE reporting

#### Screen Failures & Run-In Failures

Note the following requirement for Screen Failures: SAEs occurring after the subject has provided informed consent until the time the subject is deemed a Screen Failure must be reported to Novartis.

For subjects considered Run-In Failures, SAEs occurring after the subject has provided informed consent until the time the subject is deemed a Run-In Failure must be reported to Novartis.

